9. STATISTICAL ANALYSIS

Given the preliminary nature of this study, statistical analyses of our outcomes will not be conclusive; rather we will examine the data for trends across time rather than relying exclusively on tests of statistical significance.

9.a. Primary Outcomes

The primary outcomes of this study are: Aggression, Receipt of Behavioral Infractions, and Time Spent in Administrative Segregation (see Appendix B).

9.b. Secondary Outcomes

The secondary outcomes of this study are those measures listed as Treatment Targets in the conceptual model: Interpersonal Problem Solving, Criminal Attitudes and Associates, and Levels of Impulsivity (see Appendix B).

9.c. Statistical Methods

Treatment Targets and Study Outcomes that are collected via a standardized measure (i.e. Social Problem Solving, Criminal Attitudes and Associates, Impulsivity, and Aggression) are collected at baseline as well as during follow-up periods (see Appendix A). Study Outcomes that are collected via administrative data (i.e. receipt of behavioral infractions and time spent in administrative segregation), however, are not collected as baseline, rather are summed cumulatively over the period extending from the 3-month follow-up period through the 9-month follow-up period.

To examine the impact of T4C-MI on study outcomes that are measured dichotomously and only collected during follow-up periods (i.e. receipt of disciplinary fractions and administrative segregation), we will use chi-square tests to examine between-group differences during the post-test period. To examine between-group post-test differences when these outcomes are measured as counts (i.e. number of behavioral infractions received and days spend in administrative segregation), nonparametric tests will be used to test differences in group medians (e.g. Mann-Whitney Test) and regressions that can accommodate count data (e.g. Poisson, negative binomial) will be employed.

For Treatment Targets and Study Outcomes that are measured continuously and collected at both baseline and follow-up periods (i.e. Social problem solving, impulsivity, criminal attitudes and associates, and aggression), we will use T-tests to examine between-group differences at posttest as well as mixed effects linear models where measurement occasion at level 1 is nested within the individual at level 2.

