11. PARTICIPANT RIGHTS AND CONFIDENTIALITY

11.a. Participant Confidentiality and Security

Project data and information will be maintained at the School of Social Work (SOSW) in the Tate-Turner-Kuralt Building on the campus of the University of North Carolina at Chapel Hill. At the SOSW, a secure, password-protected computer file for all project materials will be established with access restricted to the research team. All data schedules and interview forms will be filed securely away in locked file cabinets. All personal computers are password protected and servers are located on lockable offices.

Study subjects will be assigned unique, study identifiers. A separate master list of study IDs will be kept separately. Once data collection is complete, all personal identifiers will be destroyed. Once personal identifiers are destroyed all study subjects will be identified only by a unique study identifier.

All study documents will be maintained in locked filing cabinets within locked offices. Additionally, a Certificate of Confidentiality will be obtained to protect subject information. All interviews will take place in private settings within the prison. Participants will be informed that they can choose not to answer question(s) and can stop an interview at any time.

11.b. Study Discontinuation

There are four reasons that the study staff would withdraw a person from the research intervention and study: (1) in the unlikely event that a study participant would become aggressive or combative during the research intervention or research interview they would be withdrawn from the study; (2) if a subject's participation in the research intervention or interviews caused undue levels of emotional distress, either as reported by the subject or as observed by the researchers; and (3) if a subject asks to be withdrawn or declines further participation in the research intervention or follow-up research interviews at any point (4) if a subject is transferred or released from the prison where the experimental intervention is being delivered.

12. APPENDIX A: Assessment and Data Collection

	Initial Meeting and Screening Interview*	Baseline Interview	Delivery of the Study Intervention*	Three-month follow-up Interview	Six-month follow-up Interview	Nine-month administrative records check**
Screening and Intervention Delivery						
Recruitment and Informed Consent	X					
Participant Demographic and Background Characteristics	X					

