Eligibility Determination	X					
Randomization	X					
Study intervention			X			
Data Collection						
Social Problem Solving		X		X		
Criminal Attitudes and Associates		X		X		
Impulsivity		X		X		
Aggression		X		X	X	
Behavioral Infraction**						X
Administrative Segregation**						X

*Only individuals randomized to the treatment condition are offered to participate in the intervention. The study intervention lasts between 12-14 weeks in duration

**This data is collected via administrative data, not through face-to-face interviews as is the other study data.

13. APPENDIX B: Description of Study Measures

Outcome	Measure	Description	Citation
Primary Study Outcomes			
Aggression	Aggression Questionnaire - Short Form (AQ-Short)	A 12-item measure with four subscales: physical aggression, verbal aggression, anger, and hostility. Items are scored on a 5-point Likert scale.	Bryant FB, Smith BD. Aggression Questionnaire--Short Form. Psytests. 2001. doi:10.1037/t09754-000
Behavioral Infractions	From administrative data	Prison records will be used to ascertain the number of behavioral infractions participants incur.	n/a
Administrative Segregation	From administrative data	Prison records will be used to determine the length of time participants are confined in administrative segregation.	n/a

Secondary Outcomes			
Social Problem Solving	Social Problem-Solving Inventory - Revised, Long (SPSI-R:L)	A 52-item measure of problem-solving skills and problem orientation. Items are measured on a 7-point Likert scale. It has three scales that will be used in this analysis: problem orientation, problem solving skills, and social problem-solving inventory.	D'Zurilla TJ, Nezu AM, Maydeu-Olivares A (n.d). Social Problem-Solving Inventory - Revised. Psytests. doi:10.1037/t05068-000
Criminal Attitudes and Associates	Measure of Criminal Attitudes and Associates (MCAA)	A 46-item measure. Responses are recorded in an agree/disagree format. MCAA includes four scales: attitudes toward violence, sentiments of entitlement, antisocial intent, and associates.	Mills JF, Kroner DG, Forth AE. Measures of Criminal Attitudes and Associates (MCAA): development, factor structure, reliability, and validity. Assessment . 2002 Sep;9(3):240-53. PubMed ID: 12216781

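### Infractions and segregation days are raw month 3–9 sums with no exposure term, and the plan does not say whether the records check still covers people who leave the study

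*Combined protocol and SAP*

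**What the plan says.** Section 9.a names the outcomes: "The primary outcomes of this study are: Aggression, Receipt of Behavioral Infractions, and Time Spent in Administrative Segregation". Section 9.c states that the two administrative outcomes have no baseline value and are "summed cumulatively over the period extending from the 3-month follow-up period through the 9-month follow-up period".

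Three kinds of analysis follow in 9.c:

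- Any versus none: "we will use chi-square tests to examine between-group differences during the post-test period".
- Counts, by rank: Mann-Whitney is the example given.
- Counts, by model: "regressions that can accommodate count data (e.g. Poisson, negative binomial) will be employed".

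Appendix B defines the measures as a number and a duration, with no denominator: "Prison records will be used to ascertain the number of behavioral infractions participants incur" and "Prison records will be used to determine the length of time participants are confined in administrative segregation".

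Section 11.b lists four reasons for withdrawing a person from both the intervention and the study: aggression during a session or interview, undue distress, the person's own request, and "if a subject is transferred or released from the prison where the experimental intervention is being delivered".

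The documents do not mention days at risk, person-time, an offset, a rate, or the handling of an incomplete window. They do not say whether the 9-month records check continues after withdrawal.

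**The concern.** A sum over a fixed window measures behavior only if everyone is observed for the whole window. Someone whose records end at month 4 has had a sixth of the six-month window in which to incur an infraction or a segregation day. Without a denominator, that person tends to look better than someone observed throughout.

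Two things are at stake. The arm comparison on two primary outcomes is biased if exits differ by arm. In addition, 9.d gives the pilot's main purpose as supplying what is needed for R01 power calculations, and an event rate taken from raw sums is too low whenever some windows are cut short, even if exits are balanced.

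There is one documented reason why exits could differ. The aggression rule in 11.b can be triggered in sessions as well as interviews. Both arms have the same interviews, but only T4C-MI participants are offered the 25 sessions.

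**Working it through.** The plan gives no event rate, exit rate or dispersion, so there is no stated figure to reproduce. The calculations below are illustrations under stated assumptions.

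**Inputs from the documents.** Up to 112 participants (9.d) with equal allocation (3.a), so 56 per arm. Window from month 3 to month 9 (9.c).

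**Assumptions.** Equal true rates in both arms; records stop at exit; a share *q* of an arm exits uniformly over the window, independently of behavior.

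**1. Raw ratio.** A leaver is observed for half the window on average, so mean exposure is 1 − *q*/2. The expected ratio of raw sums, T4C-MI to control, is (1 − *q*T/2)/(1 − *q*C/2).

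| Exits, T4C-MI vs control | Mean exposure | Raw ratio |
|---|---|---|
| 10% vs 10% | 0.95 / 0.95 | 1.00 |
| 20% vs 10% | 0.90 / 0.95 | 0.947 |
| 30% vs 10% | 0.85 / 0.95 | 0.895 |
| 40% vs 10% | 0.80 / 0.95 | 0.842 |

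**2. Any infraction.** With Poisson counts of mean 1 per full window, the share with at least one is 1 − [(1 − *q*)e⁻¹ + *q*(1 − e⁻¹)].

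- *q* = 10%: 1 − (0.331 + 0.063) = 60.6%.
- *q* = 30%: 1 − (0.258 + 0.190) = 55.3%.

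The chi-square comparison therefore shifts as well.

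**3. Rates for the R01.** With equal exits of 10% in both arms, mean exposure is 0.95, so each arm's rate is understated by 5%. With equal exits of 20% it is understated by 10%.

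**4. Effect of an offset.** Simulation of 1,500 trials, 56 per arm, gamma-Poisson counts with mean 1.5 and shape 1, true rate ratio 1, two-sided 0.05 level:

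| Exits, T4C-MI vs control | Ratio, no offset | Ratio, offset | False positives: NB no offset | NB offset | Mann-Whitney | Chi-square |
|---|---|---|---|---|---|---|
| None | 1.00 | 1.00 | 6.2% | 6.2% | 5.9% | 5.4% |
| 10% vs 10% | 1.00 | 0.99 | 5.5% | 4.7% | 4.9% | 5.1% |
| 30% vs 10% | 0.90 | 1.01 | 7.2% | 5.5% | 7.1% | 6.5% |
| 40% vs 10% | 0.84 | 0.99 | 11.3% | 4.1% | 11.9% | 9.7% |

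The offset brings the ratio back to about 1 when exits are unrelated to behavior. The excess of false positives is slight at 30% vs 10% and clear only at 40% vs 10%.

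**5. Comparison with sampling error.** With mean 1.5 and shape 0.7, the count variance is 1.5 + 2.25/0.7 = 4.71. The standard error of the log rate ratio is √(2 × 4.71/(56 × 2.25)) = 0.27, so a 95% interval around 1 runs from about 0.58 to 1.71. A ratio of 0.947 is ln(0.947) = −0.054, or 0.2 standard errors; 0.895 is −0.111, or 0.4. The relative standard error of one arm's mean is √(4.71/(56 × 2.25)) = 19%, against the 5–10% understatement in step 3.

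**The case against.** The strongest reply is that unequal windows are inferred. The documents describe a single records check, separate from the interviews, and participants sign an authorization for administrative data (6.b). Leaving the group or declining interviews does not by itself close a prison record, and someone moved within the state system may still be in it. The transfer-or-release reason can also be read as confined to the 12–14 weeks of delivery, which largely precede the window. All of this stands. It means that the plan is silent on coverage; it does not show that coverage is complete, and 11.b does withdraw people from the study as well as the intervention.

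A reader might infer more than the documents support:

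- **That leavers are scored as zero events.** Exits before month 3 scored as zero would give 0.80/0.90 = 0.89 or 0.70/0.90 = 0.78, but no text says that leavers are handled this way. They could equally be dropped, followed in full or counted to exit.
- **That release is a major route.** At least one year of sentence must remain at screening, against nine months of follow-up. Transfer and withdrawal matter more.
- **That the comparison is biased in favor of T4C-MI.** This needs exits that differ by arm or relate to outcome. The documents give no exit rates, and 11.b itself regards aggression in sessions or interviews as unlikely.

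Section 9 also calls the analyses inconclusive, and 9.d disclaims estimating effect sizes. That lowers the consequence for the arm comparison. It does not answer the need for usable event rates. Finally, the count models are named only as examples, so the absence of an offset is not a decision against one. Chi-square and Mann-Whitney, however, have no place for an offset.

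**Conclusion.** The point holds conditionally. The raw sums, the missing exposure term and the silence on records coverage after withdrawal are in the documents. Bias in the arm comparison follows only if records stop at exit and exits differ by arm or relate to outcome. Under the assumed uniform exits of 20% vs 10% or 30% vs 10%, the spurious ratio is about 0.95 or 0.89, which is 0.2 to 0.4 standard errors under the assumed dispersion. Equal exits unrelated to behavior do not bias the ratio but lower the estimated rates. This is a cheap improvement that should be made; it does not invalidate the pilot.

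A connected inconsistency affects the end of the window. Step Seven of 6.a places the administrative assessment nine months after release, whereas the synopsis (Study Phases, item 7) places it nine months after baseline.

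**What to change.** In 9.c and Appendix B:

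1. Collect prison records through month 9 for every randomized participant where the authorization allows, including those who leave the intervention or interviews or are transferred within the state prison system. This concerns data collection only and leaves the withdrawal rules untouched.
2. Record for each person the days in custody covered by the records between months 3 and 9.
3. Use log(days at risk) as the offset in the Poisson or negative binomial models, make these the main analysis of the two outcomes, and report rates per 100 days at risk.
4. Treat zero covered days as missing, not as zero events.
5. Keep chi-square and Mann-Whitney as supportive analyses of all participants with records. Report covered days and exit reasons by arm. Show any result restricted to full windows only as a sensitivity analysis, because it conditions on a post-randomization event.
6. State that the offset assumes a constant rate over the window and does not remove bias from exits related to aggression.

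Reconcile 6.a with the synopsis on when the nine months end.

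The cost is a few sentences plus custody start and stop dates in the same records request. The main statistical price is the constant-rate assumption.

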3. STUDY DESIGN

This study will engage a pilot effectiveness trial to examine the extent to which T4C-MI impacts its intended targets (mediating mechanisms) and outcomes among prisoners with SMI. The study will use a randomized controlled design to assign participants to one of the two study arms 1) the study intervention (T4C-MI) or 2) Standard Prison Treatment and programming. The study will take place in the North Carolina Prison system and will involve up to four facilities.

3.a. Allocation to Treatment Groups

In this study randomization will take place on site at the prison, which does not allow electronic equipment to be brought into facilities. Therefore, the study team will use a shuffled envelope to randomize participants on site at the prison. The study team will use a table of computer-generated random numbers and block randomization procedures to ensure an equal distribution of subjects to each arm of the study. Study staff will not be blinded to participant condition.

3.b. Study Duration, Enrollment and Number of Subjects

The study will be active for 4 years. Each participant will be involved for 9 months.

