The potential mediation effects of the proposed primary treatment targets on study outcomes will be explored using structural equation modelling (SEM) and generalized structural equation modelling (GSEM) frameworks to accommodate for variables that are measured both continuously and dichotomously.

9.d. Sample Size and Power

The sample will include up to 112 participants. Given the preliminary nature of this pilot study, our goals are not to fully test our hypotheses nor estimate effect sizes associated with T4C-MI. The main purpose of this R34 is to collect data on available sample size, sample attrition and sample retention and the generation of data and information necessary to conduct comprehensive power calculations for an R01. Nevertheless, here, the likelihood of detecting statistical significance will be increased due to the use of a longitudinal design with up to four measurements per subject on our treatment targets and outcome

measures. Also, our longitudinal design allows for each participant to serve as his/her own historic control, eliminating between-subjects variation and reducing standard errors, which increases power.

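### Section 9.c describes the Mann-Whitney test as a test of group medians for infractions and segregation days; it compares ranks, so a conclusion about medians would not follow from it

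*Combined protocol and SAP*

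**What the plan says.** Section 9.a names receipt of behavioral infractions and time in administrative segregation as two of the three primary outcomes. Section 9.c says both are "summed cumulatively over the period extending from the 3-month follow-up period through the 9-month follow-up period". It then plans three kinds of analysis for them:

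- For any versus none: "we will use chi-square tests to examine between-group differences during the post-test period".
- For the counts ("number of behavioral infractions received and days spend in administrative segregation"): "nonparametric tests will be used to test differences in group medians (e.g. Mann-Whitney Test").
- For the same counts: "regressions that can accommodate count data (e.g. Poisson, negative binomial) will be employed".

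Appendix B defines the infraction outcome per participant: "Prison records will be used to ascertain the number of behavioral infractions participants incur". Section 9.c states no assumption that the two arms' distributions have the same shape. It names no effect measure to accompany the rank test.

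**The concern.** The hypothesis named in Section 9.c is not the one that the named test addresses. Mann-Whitney is built on the probability that a value from one arm exceeds a value from the other. That becomes a statement about medians only when one distribution is the other moved sideways by a constant. Infractions and segregation days cannot fall below zero. If both arms include people with none, any non-zero shift would move one arm's zeros to some other value, so a pure shift is not a credible model.

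At stake is the interpretation of two primary outcomes. A results table built to this wording would set a p-value beside a difference in medians that the p-value does not test. If many participants have no events, that difference could be exactly 0 with a small p-value next to it. Section 9.d says the pilot is meant to supply information for later power calculations, and a median difference of 0 would contribute little to that.

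**Working it through.** The plan gives no power, alpha, event rate or zero share for these outcomes, so there is no figure of its own to reproduce. The check asks when the wording would produce a visibly wrong statement.

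**Inputs from the documents**
- Sample size, Section 9.d: "The sample will include up to 112 participants".
- Allocation, Section 3.a: "block randomization procedures to ensure an equal distribution of subjects to each arm of the study". Hence at most 112 / 2 = 56 per arm.

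**Inputs assumed**
- Share of participants with zero events: 20% to 80%.
- Two-sided alpha of 0.05.
- Non-zero segregation days drawn from a gamma distribution with mean 20.

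**Step 1. When is an arm's sample median 0?** With 56 people the median is the average of the 28th and 29th ordered values, so it is 0 when at least 29 people have zero events:

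P(median = 0) = P(Binomial(56, p0) ≥ 29)

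| True zero share p0 | P(sample median = 0) |
|---|---|
| 30% | 0.0005 |
| 40% | 0.05 |
| 50% | 0.45 |
| 55% | 0.73 |
| 60% | 0.92 |
| 70% | 0.999 |
| 80% | about 1 |

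The arms are independent, so the chance that both medians are 0 is the product: 0.05 × 0.92 = 0.046 at 40% versus 60%, 0.45 × 0.999 = 0.45 at 50% versus 70%, and 0.92 × 1 = 0.92 at 60% versus 80%.

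**Step 2. Among significant results, how often are both medians 0?** Simulated trials, 56 per arm, tie-corrected Mann-Whitney, 20-point gap in zeros:

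| Zeros in the two arms | Significant results with both medians 0 |
|---|---|
| 20% vs 40% | 0% |
| 30% vs 50% | 0% |
| 40% vs 60% | 0.3% |
| 50% vs 70% | 23% |
| 55% vs 75% | 57% |
| 60% vs 80% | 88% |

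Repeat runs with gamma shape 1 or 2 move these by up to three points. At 50% versus 70% the figure is below the 45% of Step 1 because significant results come mainly from trials in which the arm with fewer zeros happened to draw few of them.

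**Step 3. A different model.** With negative binomial counts (dispersion 1, rate ratio 0.5), the share of significant results with equal medians was 4%, 21%, 83% and 99% at control-arm zero shares of 40%, 50%, 60% and 70%. The dependence is the same.

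**Step 4. Is the test itself sound?** With identical distributions in both arms it rejected in 4% to 6% of trials. Type I error is intact.

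**Step 5. One constructed data set.** 56 per arm, with zeros in 31 and 45 participants. Both exceed 28, so both medians are 0. Mean counts are 47/56 = 0.84 and 20/56 = 0.36. Mann-Whitney gives p = 0.005, and the probability of superiority, P(X > Y) + 0.5 P(X = Y), is 0.63. The test detects a real difference between the distributions, and the median difference is exactly 0.

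**The case against.** The strongest reply is that this is a wording point in a pilot. Section 9 says the analyses will not be conclusive, and the plan commits to no claim about medians. Mann-Whitney is given only as an example, and the same paragraph plans chi-square tests and count regression, so a ratio of means and a percentage with any event would appear beside any rank p-value. Most of this stands, and it is why the point is minor. It does not remove the error: medians are the stated target whichever test is chosen, and Mann-Whitney is the only one named.

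Four stronger readings are tempting, and the documents do not support them.

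- *The counts will be mostly zero, so both medians will usually be 0.* No zero share or event rate is given. Section 1.a says only that prisoners with mental illness have higher infraction rates and more frequent and intense segregation than other prisoners. Section 4 requires moderate to high criminogenic risk but excludes people with assault precautions. The share could fall either side of one half.
- *The test is invalid, or the plan's conclusion is wrong.* The test keeps its size, and no conclusion is stated. Only a later report in terms of medians would be wrong.
- *The rank test ignores the outcome defined in Appendix B.* Appendix B defines each participant's count and length of time, and these are the values that Mann-Whitney ranks. It names no arm total or mean.
- *The test can favour an arm when mean days are equal.* It can: with 80% versus 60% zeros and 20% × 40 = 40% × 20 = 8 mean days per arm, it rejects in about 45% of trials. But the distributions do differ there, so these are not false positives, and the case needs a 20-point gap exactly offset by a doubling of days among those segregated. With equal means and a 10-point gap, rejection was 10% to 16%.

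**Conclusion.** The point holds as a mismatch between the named test and the hypothesis attached to it, for the count form of two of the three primary outcomes. That part needs no assumed event rate. The visible consequence, a significant result with both medians 0, is conditional. It is essentially absent when zeros are 40% versus 60% or lower, happens in roughly a quarter of significant results at 50% versus 70%, and becomes the usual case at 60% versus 80%. These figures rest on 56 per arm, a 20-point gap and the assumed distribution of days. Sample size and error rates are not affected. The severity is low: worth correcting because it is cheap. Which of the planned analyses should lead is a separate choice about hierarchy, and this point does not settle it.

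**What to change.** In Section 9.c, replace the phrase about testing differences in group medians with: *test whether values tend to be larger in one arm than in the other (e.g. Mann-Whitney test), reported as the probability of superiority, P(X > Y) + 0.5 P(X = Y), with a 95% confidence interval*. Do not attach a median difference to this p-value. Present the result beside the ratio from the planned count regression and the percentage with any event from the planned chi-square analysis. The cost is one sentence in Section 9.c and one column in the results table, with no new data and no change in sample size.

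### Section 9.c names no baseline adjustment and no lead analysis for aggression and the three treatment targets, which costs precision

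*Combined protocol and SAP*

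**What the plan says.** Section 9.c of the combined protocol and SAP groups four interview measures together ("i.e. Social problem solving, impulsivity, criminal attitudes and associates, and aggression") and states that they "are collected at baseline as well as during follow-up periods". For all four, the analysis is: "we will use T-tests to examine between-group differences at posttest as well as mixed effects linear models". The mixed model has two levels, with repeated occasions inside each participant. No baseline covariate, arm or time effect, arm-by-time term, constraint on baseline means, covariance structure or lead time point is given. Nothing says which of the two analyses leads.

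The schedule in Appendix A shows two occasions for each target, baseline and 3 months (for example "Social Problem Solving X X"). It shows three for aggression: baseline, 3 and 6 months ("Aggression X X X").

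On size, Section 9.d says: "The sample will include up to 112 participants". Section 3.a plans "block randomization procedures to ensure an equal distribution of subjects to each arm of the study". Section 9.d also argues that precision is gained because each participant acts as his or her own control. It gives no alpha, power, effect size, SD or correlation. Section 9 describes the analyses as not conclusive.

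**The concern.** All four measures have a baseline score, and the plan does not show that it will be used well. The t-test does not use it. The mixed model might, but its form is left open. The own-control reasoning in 9.d points to the usual arm-by-time form, which compares changes from baseline. A change score corrects for the whole baseline difference, which is too much unless the correlation is close to 1.

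At stake is the precision of the arm difference for one primary and all three secondary outcomes. There is also a choice problem: two analyses of the same data with no stated lead allow either to be presented as the result. Finally, Section 9.d says that a main purpose is to supply inputs for power calculations for a larger trial. Those need the correlation and the adjusted residual variance, which 9.c does not ask for.

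**Working it through.** **Inputs from the documents.** Up to 112 participants with equal allocation: 112/2 = 56 per arm. Occasions as in Appendix A. The plan gives no power figure to reproduce.

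**Assumptions.** Equal SD at each occasion, complete data, two-sided alpha 0.05, a true effect of 0.5 SD, and r from 0.4 to 0.6. The documents supply none of these.

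**Step 1: what the mixed model tests.** With two occasions, complete data and a random intercept, the arm-by-time term equals the difference in mean change. In a simulated data set with r = 0.5, both gave −0.2404 (SE 0.1649). With three occasions, as for aggression, the 6-month arm-by-time estimate still equalled the difference in change from baseline to 6 months. Its SE differed because the residual variance is pooled over occasions (0.189 against 0.200 at r = 0.5). That model also yields a 3-month contrast.

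**Step 2: variance of the arm contrast at one follow-up visit.** In units of 2·SD²/n per arm:
- post-test t-test: 1
- change score: 2(1 − r)
- baseline-adjusted: 1 − r²

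Since 1 − r² = (1 − r)(1 + r), the adjusted variance is below 2(1 − r) whenever r < 1, and below 1 whenever r > 0. Below r = 0.5 the change score is less precise than ignoring baseline.

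**Step 3: power at 0.5 SD, from the noncentral t with 56 per arm.**

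| r | Variance factors (t-test / change / adjusted) | Power (t-test / change / adjusted) |
|---|---|---|
| 0.4 | 1 / 1.20 / 0.84 | 0.75 / 0.67 / 0.82 |
| 0.5 | 1 / 1.00 / 0.75 | 0.75 / 0.75 / 0.86 |
| 0.6 | 1 / 0.80 / 0.64 | 0.75 / 0.83 / 0.91 |

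The 95% CI half-width is 1.96·√(2·factor/56). At r = 0.6 it is 0.37, 0.33 and 0.30 SD. Put as sample size, at r = 0.5 an adjusted analysis of 112 × 0.75 = 84 participants is as precise as either other analysis of 112. Dropout would lower all three powers.

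**Step 4: aggression, mean of the 3- and 6-month scores.** Assuming the same r between all pairs of visits, the factors are (1 + r)/2 for the post-test, (1 + r)/2 + 1 − 2r for change, and (1 + r)/2 − r² for adjusted. At r = 0.5 these are 0.75, 0.75 and 0.50. The change variance is 1.67, 1.50 and 1.36 times the adjusted variance at r = 0.4, 0.5 and 0.6.

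**Step 5: two tests with no stated lead, two-occasion targets.** With no effect, the t-test and change-score statistics correlate at (1 − r)/√(2(1 − r)) = √((1 − r)/2), which is 0.55 at r = 0.4 and 0.45 at r = 0.6. The bivariate normal chance that at least one is significant at 5% is 8.9% and 9.2%, so about 9%.

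**Step 6: baseline after disclosure.** By Section 6.a, baseline follows the participant's learning the assignment. Suppose disclosure shifts one arm's baseline score by s (in SD units). The size of the bias is then 0 for the t-test, r·s for the adjusted contrast and s for the change score. Compared with the t-test, adjustment saves variance r²·2/56 and adds squared bias r²s². These are equal at s = √(2/56) = 0.19 SD, whatever r is.

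**The case against.** Three objections carry weight.

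First, a reader might infer that the mixed model is only a change-score test for every measure. The documents do not support that. Aggression has three occasions, and 9.c never writes down an arm-by-time term. A mixed model with the two arms' baseline means held equal comes close to the adjusted analysis (−0.469 against −0.460 in a simulated two-occasion example with r = 0.7), and a mixed model can also use incomplete cases. What stands is that the model is under-specified and that its usual form compares change.

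Second, a reader might infer that both analyses waste the baseline data. Only the t-test ignores it. The change score uses it less efficiently, and the loss shrinks as r rises: its variance exceeds the adjusted variance by the factor 2/(1 + r), which is 1.33 at r = 0.5 and 1.18 at r = 0.7.

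Third, baseline is collected after disclosure, by staff who are not blinded (Section 3.a). The post-test t-test is the one analysis that a disclosure shift in baseline cannot bias, so adjustment is not better in every respect. This stands. It limits the fix without removing it, since the change-type model already in prospect would carry the larger bias.

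It is also fair to say that this is a pilot that disclaims firm conclusions. That lowers the stakes of any single test. It does not lower the value of precise estimates, because the plan looks to trends more than to significance.

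**Conclusion.** The point holds as a matter of precision and specification. For four measures with a baseline score, 9.c plans one analysis that ignores it and one whose handling of it is unstated, with no lead between them. Under the assumptions above (56 per arm, 0.5 SD, r from 0.4 to 0.6, complete data), a baseline-adjusted analysis has power 0.82 to 0.91, against 0.75 for the t-test and 0.67 to 0.83 for the change score. For the two-occasion targets, the chance of at least one significant result with no effect is about 9%; that figure has not been worked out for aggression.

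The ordering of the variances holds for any r between 0 and 1, while the size of the gain depends on r, which the documents do not give. A reader might infer that the sample of 112 is shown to be inadequate or that a stated figure is wrong. Neither follows, because the plan sets no power target. The advantage over the t-test in mean squared error also depends on a disclosure shift in baseline of less than about 0.19 SD, and the documents do not let that shift be estimated.

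**What to change.** In Section 9.c, name one baseline-adjusted model as the lead analysis of the four interview measures:

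- **Three targets:** regress the 3-month score on arm and the participant's own baseline score.
- **Aggression:** fit a longitudinal model of the 3- and 6-month scores with baseline as covariate, visit as a category, arm-by-visit terms and an unstructured covariance. State which contrast leads (3 months, 6 months or their mean).
- **Reporting:** give the arm difference with its 95% CI, and the observed r for planning the later trial.
- **Alongside:** report the unadjusted post-test difference and the baseline means by arm, and state that baseline followed disclosure of the assignment. If baseline is moved before randomization, this caveat falls away.

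Section 9.d speaks of up to four measurements per subject on targets and outcomes. Reconcile this with the two or three interview occasions in Appendix A.

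The cost is a rewritten paragraph, with no new data or visits. The downside is the possible bias r·s while baseline stays after disclosure, which is why the unadjusted result is reported beside the lead analysis. Moving baseline earlier would be a change of procedure and is not needed for the rewording.
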